14.2. Sample Size Justification

Phase I of this study was not powered to test non-inferiority of O1D relative to P1 with respect to the primary endpoints. However, data collected during Phase I of the study will be used to power Phase II to test for superiority of the O1D relative to P1 with respect to *Overall comfort*,

Clinical Study Protocol

Johnson & Johnson Vision Care, Inc.

Comfort at the End of the Day and Dryness at the End of the Day. Based on these results from testing for non-inferiority for each primary endpoint from the interim analysis (Phase I analysis), the sample size will be calculated to test all three primary hypotheses for superiority with at least 80% power. This will be calculated using an approximation of the power of an F-test derived from the non-centrality parameter calculated from the observed F-statistic from the generalized linear model described in Section 14.5 for Phase I.⁹ If the sample size calculation for Phase II exceeds 300 then the Sponsor reserves the right to terminate the study. Alpha will be adjusted as described in Section 14.4. Complete details of the sample size calculation for Phase II are described in Section 14.5.

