Sample Size	Approximately 65 subjects will be enrolled in Phase I with a target of completing 60 subjects. An interim analysis based on Phase I will determine the number of subjects to be enrolled into Phase II, with a maximum of 300 additional subjects.
Study Duration	The timeframe between anticipated First Subject First Visit (FSFV) and anticipated Last Subject Last Visit (LSLV) is 6 months.
Anticipated Study Population	Habitual daily disposable soft contact lens wearers in the age range of 18 to 40.
Eligibility Criteria - Inclusion	
Inclusion Criteria following Screening
 
The subject must:
 
 1. Read, understand, and sign the STATEMENT OF INFORMED CONSENT and receive a fully executed copy of the form. 2. Appear able and willing to adhere to the instructions set forth in this clinical protocol. 3. Be between 18 and 40 (inclusive) years of age at the time of screening. 4. By self-report, habitually wear soft spherical contact lenses in both eyes in a daily disposable wear modality. Habitual wear is defined as a minimum of 8 hours of wear per day, for a minimum of 4 days per week during the past 4 weeks. 5. By self-report, typically uses computer screens and other digital devices (phones, tablets) at least 30 hours per week. 
Inclusion Criteria at Baseline Evaluation
 
 6. The vertex-corrected best spherical distance refraction (rounded to nearest 0.25 D) must be between -1.00 and -4.00 DS (inclusive) in each eye. 7. The magnitude of the cylinder component of the subject's distance refraction must be 1.00 DC or less. 8. The subject must have best corrected visual acuity of 20/25 or better in each eye.

Clinical Study Protocol

Johnson & Johnson Vision Care, Inc.

Eligibility Criteria – Exclusion	
Potential subjects who meet any of the following criteria will be excluded from participating in the study:

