4.2. Study Design Rationale

A two-phase adaptative approach utilizing a 2x2 crossover was chosen as the most optimal design to achieve the study objectives. An adaptive design was considered since no historical data was available for P1 with respect to the primary endpoints. Therefore, incorporating an adaptive approach into this study will facilitate the ability to estimate the number of subjects needed to demonstrate the primary hypotheses. This approach can help reduce the number of subjects and the amount of time to conduct a study to achieve the same results as compared to conducting a separate pilot and confirmatory study. Furthermore, a 2x2 crossover was also implemented into the study design since this can help reduce the number of subjects required to complete a study since participants in a crossover study act as their own Control. Moreover, subjects acting as their own control can help reduce the effects of potential confounding factors between subjects, such as vision correction, age and race.⁶ All crossover studies have an inherent risk of observing a carryover effect. To help mitigate the risk of a carryover effect, subjects will undergo a washout period for approximately 1-week (6 to 8 days) between study lenses. During the washout period subjects will wear either their spectacles or habitual lenses.

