14.4. Level of Statistical Significance

All type I error adjustments utilized in this study were calculated using a Bonferroni¹⁰ correction.

Primary hypotheses in Phase I will be tested using a familywise type I error rate of 5%; each hypothesis will be tested using an individual type I error rate of 1.67%.

Hypotheses in Phase II will be tested using the following strategy:

Primary hypotheses will be tested using a familywise type I error rate of 5%; each hypothesis will be tested using an individual type I error rate of 1.67%. All primary hypotheses must be met in order to test any secondary hypotheses. Secondary hypotheses were grouped according to item semantic similarities. Each secondary hypothesis group will be tested using an overall type I error rate of 5% and in a sequential order. Each preceding secondary hypothesis group must be fully met in order to continue testing the remaining secondary hypotheses. Exploratory hypotheses will only be tested if all primary and secondary group 2 hypotheses are met.

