$$\begin{aligned}H_0: OR &\leq 0.67 \\H_a: OR &> 0.67\end{aligned}$$

Where, the OR represents the odds of having a more positive experience (Excellent or Very Good) while wearing O1D compared to P1. Non-inferiority of O1D relative to P1 will be concluded if the lower limit of the 97.5% CI is above 0.67 (using 10% as non-inferiority margin and assuming a reference proportion of 0.5).

Clinical Study Protocol

Johnson & Johnson Vision Care, Inc.

Sample size Estimation for Phase II

If non-inferiority is demonstrated for the primary endpoints, the sample size required to test superiority for each primary endpoint will be estimated. The odds ratio and the cumulative log-odds from the model described above for each endpoint will be used to create a new dataset with the same structure and design as Phase I. This new dataset will then be analyzed using the same model. The statistical power of each endpoint will be calculated using the F-statistics as $\text{Power} = P(F[F_{\text{crit}}, v, ncp] > F_{\text{crit}})$; where F_{crit} is the critical value of the central F distribution ($F_{\text{crit}} = F_{\text{numdf}, \text{dmdf}, 0, \alpha}$) under H_0 (H_0 : centrality param = 0), v is the magnitude of the departure from H_0 and ncp is the non-centrality parameter (Stroup).⁹

Phase II

Overall comfort, Comfort at the end of the day, and Dryness at the end of the day

Subjective responses to each primary endpoint will be grouped as: $aval=1$ is a subject responds' 'Excellent' or 'Very Good', $aval=2$ is a subject responds' 'Good' and $aval=3$ if a subject responds' 'Fair' or 'Poor'. $Aval$ will be analyzed separately for each primary endpoint using a generalized linear mixed model with a multinomial distribution and the cumulative logit as the link function. In each model, sequence of lens wear, period and lens type will be included as fixed effects. Site and subject nested within site will be included as a random effect. Errors between measurements within the same subject across study periods will be modeled using an unstructured covariance (UN) structure. Comparisons between O1D and P1 will be carried out using 1-sided 97.5% confidence intervals (CIs) constructed for the odds ratio (O1D over P1). Superiority of O1D relative to P1 will be concluded if the lower limit of the 97.5% CI is above 1.

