14.8. Interim Analysis

This is a two-phase adaptive approach utilizing stopping rules. Approximately 65 subject will be enrolled in Phase with a target of 60 to complete. An interim analysis will be performed after all subjects have completed Phase I on primary endpoints only. Data from Phase I will be utilized to calculate the number of subjects required to complete Phase II to achieve all primary hypotheses with at least 80% power. However, maximum enrollment for Phase II can be no more than 300 subjects (based on resources and study timing). After reviewing the results from the interim analysis, the study may be stopped prior to beginning enrollment for Phase II for one of the following reasons:

1. Lack of efficacy with respect to primary endpoints (results are inconclusive)
2. Required sample size too large to achieve primary endpoints

Full details regarding the planned interim analysis are located in Section 14.5 above. Information about how the sample size calculations for Phase II will be conducted is located in Section 14.2. Addition safety endpoints such as adverse events, slit lamp findings and lens fitting characteristics may also be descriptive summarized and provided.

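### The 80% power stated for Phase II holds per endpoint and only if the Phase I estimates are exactly true; it is not the power to meet all three primary hypotheses

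*Combined protocol and SAP*

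**What the plan says.** **Effect used for sizing.** Section 14.2 takes Phase II power from an F-test approximation "derived from the non-centrality parameter calculated from the observed F-statistic from the generalized linear model described in Section 14.5 for Phase I". Section 14.5 gives the mechanics: "The odds ratio and the cumulative log-odds from the model described above for each endpoint will be used to create a new dataset", which is then analysed with the same model. No shrinkage, lower bound, minimum relevant odds ratio or minimum Phase II size is given.

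**Information behind it.** The synopsis states: "Approximately 65 subjects will be enrolled in Phase I with a target of completing 60 subjects". Section 4.2 adds that "no historical data was available for P1 with respect to the primary endpoints".

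**What is promised.** Section 14.2: "the sample size will be calculated to test all three primary hypotheses for superiority with at least 80% power". Section 14.8: Phase I data will be used to "calculate the number of subjects required to complete Phase II to achieve all primary hypotheses with at least 80% power". Section 14.5, however, computes power singly: "The statistical power of each endpoint will be calculated using the F-statistics".

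**Continuation.** Section 14.5 sizes Phase II only if non-inferiority is shown on the primary endpoints. Sections 14.2 and 14.8 let the sponsor stop if the calculated number exceeds 300 or results are inconclusive, and cap Phase II at 300. Stopping is discretionary in both sections.

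**Alpha.** Section 14.4 says "each hypothesis will be tested using an individual type I error rate of 1.67" percent, while Section 14.5 decides superiority on a one-sided 97.5% confidence limit.

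**The concern.** Two gaps separate the calculation from the claim.

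1. The calculation returns 80% only if the Phase I point estimate equals the true effect. With about 60 completers and no earlier data on the control lens, that estimate is noisy. Stopping when the calculated number is large also tends to keep the favourable estimates.
2. Power is computed for each endpoint, while the wording speaks of all three. Section 14.4 requires all three before any secondary hypothesis is tested, so joint power is the figure that matters for the testing sequence.

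Up to 300 further subjects could be enrolled on a power statement that the method does not deliver. A failed superiority test might then be read as absence of a difference when Phase II was too small to show one.

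**Working it through.** **Inputs from the plan.** 60 Phase I completers; 80% target; cap of 300; non-inferiority limit for the odds ratio 0.67; Phase II success if the one-sided 97.5% lower limit exceeds 1.

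**Assumptions.** The plan gives no effect size, so the truth is expressed as the number of completers that really gives 80% power per endpoint (the true need). Also assumed: three equal endpoints, estimates correlated 0.7 (range 0.5-0.9), N set by the weakest endpoint, SE of the Phase I log odds ratio 0.244-0.345, and Phase II analysed on its own data. Sizing and decision both use one-sided 2.5% unless stated.

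**Step 1: the plan's own figure.** With Phase I statistic Z, the plug-in size is N = 60 × (1.96 + 0.842)² / Z² = 60 × 7.85 / Z² = 471 / Z². Z = 1.4, 2.0 and 2.5 give N = 241, 118 and 76, each with 80% power if the observed effect is the true one. So 80% is reproduced by construction, under that condition only.

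**Step 2: per endpoint versus all three.** With effects known exactly and 80% for each endpoint, the probability of meeting all three is 61%, 66% and 72% at correlations 0.5, 0.7 and 0.9.

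**Step 3: noise in the input.** For a 1-df effect the expected F is about the true non-centrality plus 1. At 60 subjects the non-centrality is 7.85 × 60 / (true need) = 4.71 at 100 and 1.57 at 300. A single endpoint's F is therefore inflated on average by 1/4.71 = 21% to 1/1.57 = 64%. Taking N from the weakest of three endpoints offsets part of this, so the net effect has to be simulated.

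**Step 4: the continuation rule.** N ≤ 300 needs Z² ≥ 471/300 = 1.57, so Z ≥ 1.25. Non-inferiority needs Z > 1.96 − 0.400/SE (ln 0.67 = −0.400), which is 0.32 at SE 0.244 and 0.80 at SE 0.345. If the study stops above 300, the size rule is the binding one. If it continues at 300, non-inferiority is the binding one and the results depend on the SE.

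**Step 5: simulated power given continuation** (200,000 or more draws, correlation 0.7).

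| True need per endpoint | Stop above 300: per endpoint | Stop above 300: all three | Continue at 300: per endpoint | Continue at 300: all three |
|---|---|---|---|---|
| 100 | 79% | 67% | - | - |
| 150 | 71% | 58% | 78-81% | 68-72% |
| 200 | 64% | 49% | 73-78% | 60-66% |
| 300 | 52% | 35% | 62-68% | 46-52% |

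In the last two columns the lower figure is for SE 0.345 and the higher for SE 0.244. Under the stopping rule, correlations of 0.5-0.9 move the all-three figures to 67-68%, 57-60%, 47-51% and 32-39%. Using one-sided 1.67% for both sizing and decision changes results by about 1 point.

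**Step 6: another reading of alpha.** Sizing with a two-sided F-test at 1.67% (z = 2.394) while deciding on the 97.5% limit multiplies N by (2.394 + 0.842)² / 7.85 = 10.47 / 7.85 = 1.33. Per-endpoint power becomes 77/69/56% with stopping and 86/81/70% with continuation at 300 (SE 0.3), for true need 150/200/300. Joint power with continuation is still about 54-77%.

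**The case against.** The strongest reply has five parts.

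- **The condition is disclosed.** Section 14.2 says that the power comes from the observed F-statistic, and Section 4.2 explains why nothing better was available. That is fair, and it lowers the severity. But neither 14.2 nor 14.8 attaches the condition to the 80%, and the step from each endpoint to all three is not disclosed at all.
- **Stopping above 300 is optional.** A reader might infer that the study continues only when the effect looks large. The documents do not support that: the sponsor may also proceed at 300. Both cases are therefore shown. Whenever the calculated N exceeds 300, running 300 is below 80% by the plan's own formula.
- **N is not usually too small.** A reader might infer that it is. Because the weakest endpoint sets N, at true need 60 and 100 the calculated N falls short in only about 34% and 44% of continuing studies, and per-endpoint power is 84% and 79%. This limits the concern to moderate effects for single endpoints.
- **The Phase I model may push N upward.** As written it has fixed effects only, while the Phase II model adds a random subject effect. With an assumed within-subject correlation of 0.3, per-endpoint power under stopping rises to 78/70/57%, or 83/75/61% with the 1.67% F-test sizing as well. Joint power cannot exceed these, so it stays below 80% at true need 200 and 300. The magnitudes do move with this assumption.
- **Pooling Phase I into the final test would help.** Joint power given continuation would then be about 73-99.8% for true need 60-300. No section provides for pooling, and it would raise a type I error question.

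**Conclusion.** The point holds for the power claim. As written, the 80% is a per-endpoint figure conditional on the Phase I estimates being the truth, and Sections 14.2 and 14.8 present it as a property of Phase II for all three hypotheses. The gap between per-endpoint and joint power (61-72% with effects known) depends only on the assumed correlation. The further loss from estimation error depends on the assumed true effects, correlation, SE, alpha reading and stopping behaviour. At true need of 150 or more, joint power stayed below 80% under one-sided 2.5% sizing with either stopping or continuing, and under 1.67% F-test sizing with continuation at 300.

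With Phase II tested on its own data, the risk is a failed superiority test; a reader should not infer an inflated type I error or a safety problem from this point. Severity: should-fix.

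**What to change.** 1. In Sections 14.2 and 14.8, restate the 80% as per-endpoint power conditional on the Phase I estimates being the true effects.
2. Compute and state the power to meet all three primary hypotheses.
3. Before Phase I data are seen, add a table of simulated power given continuation over a grid of true odds ratios, endpoint correlations and SEs. Show it both for stopping above 300 and for continuing at 300.
4. Use in that table the one alpha that the plan will apply to sizing and decision, which means reconciling the 1.67% in Section 14.4 with the 97.5% limit in Section 14.5.

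The cost is protocol and SAP wording plus one simulation; the stated power will look less favourable.

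A bias-reduced sizing input, such as the observed F minus 1 or a lower confidence bound on the log odds ratio, is an option for the sponsor to weigh within the existing cap. With F minus 1 and continuation at 300, per-endpoint power is 86/83/72% against 82/78/68% for plug-in sizing at the cap (SE 0.244), a gain of 4-5 points. Joint power is 79/73/57% at SE 0.244 and 77/71/55% at SE 0.30, so this does not by itself restore 80% for all three. Making continuation at 300 mandatory would be a design change, not a wording change, since Section 14.8 bases the cap on resources and timing.

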14.3. Analysis Populations

Safety Population:

All subjects who were administered any test article excluding subjects who drop out prior to administering any test article. At least one observation should be recorded.

Per-Protocol Population:

All subjects who have successfully completed all study visits and did not substantially deviate from the protocol as determined by the trial cohort review committee prior to database hard lock (Per-Protocol Population). Justification of excluding subjects with protocol deviations in the Per-Protocol Population set will be documented in a memo to file.

Intent-to-Treat (ITT) Population:

All randomized subjects regardless of actual treatment or deviation from protocol. At least one observation should be recorded.

14.4. Level of Statistical Significance

All type I error adjustments utilized in this study were calculated using a Bonferroni¹⁰ correction.

Primary hypotheses in Phase I will be tested using a familywise type I error rate of 5%; each hypothesis will be tested using an individual type I error rate of 1.67%.

Hypotheses in Phase II will be tested using the following strategy:

Primary hypotheses will be tested using a familywise type I error rate of 5%; each hypothesis will be tested using an individual type I error rate of 1.67%. All primary hypotheses must be met in order to test any secondary hypotheses. Secondary hypotheses were grouped according to item semantic similarities. Each secondary hypothesis group will be tested using an overall type I error rate of 5% and in a sequential order. Each preceding secondary hypothesis group must be fully met in order to continue testing the remaining secondary hypotheses. Exploratory hypotheses will only be tested if all primary and secondary group 2 hypotheses are met.

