2.3. Hypotheses

After phase I, the planned interim analysis will only test the primary hypotheses. If the study continues to phase II, all hypotheses may be tested. See full details about the strategy for testing study hypotheses in Section 14.4.

Primary Hypotheses – Phase I

After approximately one week of wear, O1D will have non-inferior performance to P1 with respect to each of the following endpoints:

1. Overall comfort
2. Comfort at the end of the day
3. Dryness at the end of the day

A non-inferiority margin of 10% will be used.

Clinical Study Protocol

Johnson & Johnson Vision Care, Inc.

Primary Hypotheses – Phase II

After approximately one week of wear, O1D will have superior performance to P1 with respect to each of the following endpoints:

1. Overall comfort
2. Comfort at the end of the day
3. Dryness at the end of the day

All primary hypotheses must be met in order to begin testing any secondary hypotheses.

Secondary Hypotheses

Secondary Group 1: Comfort Performance

After approximately one week of wear, O1D will have superior performance to P1 with respect to the endpoint: Comfort throughout the day.

Secondary Group 2: Digital Performance

After approximately one week of wear, O1D will have superior performance to P1 with respect to each of the following endpoints:

- a. Comfort while using digital devices
- b. Dryness while using digital devices

Secondary Group 3: Performance at Lens Fitting

After approximately one week of wear, O1D will have non-inferior performance to P1 with respect to each of the following endpoints:

- a. Lens awareness upon insertion
- b. Comfort upon insertion

A non-inferiority margin of 10% will be used.

Secondary Group 4: Lens Handling Performance

After approximately one week of wear, O1D will have non-inferior performance to P1 with respect to each of the following endpoints:

- a. Overall ease of handling
- b. Ease of insertion
- c. Ease of removal

A non-inferiority margin of 10% will be used.

Exploratory Hypotheses

All primary and secondary group 2 hypotheses must be met in order to test exploratory hypotheses.

Clinical Study Protocol

Johnson & Johnson Vision Care, Inc.

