14.5. Primary Analysis

Phase I (Interim Analysis)

Overall comfort, Comfort at the end of the day, and Dryness at the end of the day

Clinical Study Protocol

Johnson & Johnson Vision Care, Inc.

Subjective responses to each primary endpoint will be grouped as: $aval=1$ is a subject responds' 'Excellent' or 'Very Good', $aval=2$ is a subject responds' 'Good' and $aval=3$ if a subject responds' 'Fair' or 'Poor'. $aval$ will be analyzed separately for each primary endpoint using a generalized linear model with a multinomial distribution and the general logit as the link function. In each model, sequence of lens wear, period, lens type and site id will be included as fixed effects. Prior to fitting the final models for the primary endpoints, allocation of subjects' completion between sites will be evaluated. If a difference of more than 30% is observed between sites, a likelihood ratio test for homogeneous variance will be conducted using a generalized linear mixed model with a multinomial distribution and the general logit as the link function. Comparisons between O1D and P1 will be carried out under the final model using 1-sided 97.5% confidence intervals (CIs) constructed for the odds ratio (O1D over P1).

The Model:

Let $aval_{ijkl} = (aval1_{ijkl}, aval2_{ijkl}, aval3_{ijkl})$ denote the rating for l^{th} subject at the m^{th} site assigned to the k^{th} sequence for the i^{th} study lens during the j^{th} study period ($i=1, 2$; $j=1, 2$; $k=1, 2$; $l=1, \dots, n_m$; $m=1, \dots, 10$). Possible values of $aval_{ijkl}$ are $aval_{ijkl}=1$ if a subject responds: 'Excellent' or 'Very Good', $aval_{ijkl}=2$ if a subject responds: 'Good' and $aval_{ijkl}=3$ if a subject responds: 'Fair' or 'Poor'. The Likelihood will be constructed as follows:

$$\begin{aligned}aval_{ijkl} &\sim \text{Multinomial}(p1_{ijkl}, p2_{ijkl}, p3_{ijkl}) \\p1_{ijkl} &= aval1_{ijkl} \\p2_{ijkl} &= aval2_{ijkl} - aval1_{ijkl} \\p3_{ijkl} &= 1 - \sum_{X=1,2} pX_{ijkl}\end{aligned}$$

$$\text{Logit}(avalX_{ijkl}) = \beta_0 + \beta_1 * sequence_k + \beta_2 * period_j + \beta_3 * lens_{i[j,k]} + \beta_4 * Site_m$$

Where, β_0 is the intercept for $X=1, 2, 3$; $sequence_k=1$ if O1D/P1 and $sequence_k=0$ if P1/O1D; $period_j=1$ if first period and $period_j=0$ if second period; $lens_{i[j,k]}=1$ if O1D and $lens_{i[j,k]}=0$ if P1.

Hypothesis Testing

Hypothesis testing will be conducted separately for each primary endpoint as follows:

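### Section 14.4 tests each primary hypothesis at 1.67%, but Section 14.5 decides each one on a 1-sided 97.5% confidence bound, which is a 2.5% test; the two must be reconciled

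*Combined protocol and SAP*

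**What the plan says.** Section 14.4 applies Bonferroni corrections throughout. For the primaries, in Phase I and again in Phase II, it gives a familywise rate of 5% and then: "each hypothesis will be tested using an individual type I error rate of 1.67"%. It does not say whether these rates are 1-sided or 2-sided.

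Section 14.5 carries out each primary comparison "using 1-sided 97.5% confidence intervals (CIs) constructed for the odds ratio (O1D over P1"). In Phase I, non-inferiority is concluded if the lower limit exceeds 0.67. In Phase II: "Superiority of O1D relative to P1 will be concluded if the lower limit of the 97.5% CI is above 1".

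On sizing, Section 14.2 says "Alpha will be adjusted as described in Section 14.4". The power formula in Section 14.5 uses a critical F value at a level alpha, with no number given. The aim in Section 14.2 is that "the sample size will be calculated to test all three primary hypotheses for superiority with at least 80% power", while Section 14.5 computes power endpoint by endpoint. On the limit, Section 14.2 adds: "If the sample size calculation for Phase II exceeds 300 then the Sponsor reserves the right to terminate the study".

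No section states outright whether the study succeeds on any one primary or only on all three. Section 2.3 does say: "All primary hypotheses must be met in order to begin testing any secondary hypotheses".

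**The concern.** Sections 14.4 and 14.5 give different significance levels for the same test. Whoever runs the analysis must choose between them, and as the text stands that choice could be made after the data are seen.

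In Phase I the discrepancy moves only the gate to Phase II: "If non-inferiority is demonstrated for the primary endpoints, the sample size required to test superiority for each primary endpoint will be estimated". In Phase II it bears on the superiority claim itself, and on everything after it, because the secondary hypotheses open only once all primaries are met. The sizing rule inherits the same ambiguity through its reference to Section 14.4.

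**Working it through.** **Inputs.** Familywise 5%, three primaries and 1.67% each (Section 14.4); 1-sided 97.5% interval (Section 14.5); 80% power and the 300-subject limit (Section 14.2).

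**1. The plan's own figure.** 0.05 / 3 = 0.01667, so the 1.67% reproduces as a Bonferroni share.

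**2. Does any reading of sidedness match?** Compare the tail area of each reading of 1.67% with that of each reading of the 97.5% interval.
- 1.67% 1-sided against the interval as written (1-sided): 0.0167 against 0.0250.
- 1.67% 1-sided against the interval read as 2-sided: 0.0167 against 0.0125.
- 1.67% 2-sided against the interval as written: 0.0083 against 0.0250.
- 1.67% 2-sided against the interval read as 2-sided: 0.0083 against 0.0125.

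None match. Reading the 5% as 2-sided gives 2.5% in one tail only if nothing is split among the three tests, and Section 14.4 does split it.

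**3. Matching bounds.** 1 − 0.05/3 = 98.33% (z = 2.128) if the 5% is 1-sided; 1 − 0.05/6 = 99.17% (z = 2.394) if it is 2-sided. The stated 97.5% has z = 1.960.

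**4. Contradictory band.** A 1-sided p from 0.0167 (or 0.0083) to 0.025 passes Section 14.5 and fails Section 14.4.

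**5. Familywise error.** This depends on the success rule and on sidedness, neither of which is stated.
- Any one primary may be claimed, 5% 1-sided: the bound is 3 × 2.5% = 7.5%. With independent statistics it is 1 − 0.975³ = 7.3%. For three equally correlated normal statistics (correlations assumed) it is 6.3% at 0.5, 5.5% at 0.7 and 4.9% at 0.8, crossing 5% at about 0.79.
- Any one primary may be claimed, 5% 2-sided: the allowance in the favourable direction is 2.5%, so the 0.79 threshold does not apply.
- All three required: a false overall claim needs at least one true null hypothesis to be rejected at 2.5%, so the error is at most 2.5% with no split.

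**6. Sizing.** Normal approximation, 80% power per endpoint, N relative to a 1-sided 2.5% test:
- 1.67% 1-sided: (2.128 + 0.842)² / (1.960 + 0.842)² = 1.124, about 12% more.
- 1.67% entered directly as the alpha of an F-test with one numerator degree of freedom, which makes it 2-sided: (2.394 + 0.842)² / (1.960 + 0.842)² = 1.334, about 33% more.

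Measured at the 2.5% rule, the limit of 300 then acts like 300 / 1.124 = 267 or 300 / 1.334 = 225 subjects.

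**The case against.** The strongest reply is that all three primaries are required, so nothing is inflated. Section 2.3 hypothesises superiority on each endpoint and makes all of them a condition for secondary testing. Section 14.2 sizes for all three, and Section 14.8 speaks of achieving all primary hypotheses. No section authorises a claim on a single endpoint. This carries real weight. A reader might infer from the mismatch that the trial runs at 7.5% instead of 5%. The documents do not support that: the figure needs both a 1-sided 5% and a single-endpoint success rule, and the text leans the other way on the second. Yet the same reading makes the 1.67% split redundant, so Section 14.4 would still be wrong, and no section declares the endpoints co-primary.

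A reader might also infer that Phase II would be too small. On the text it is the reverse: sizing at the stricter level and testing at the looser one leaves a cushion.

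Finally, Sections 14.1 and 14.10 refer to a stand-alone SAP that is not among the documents supplied. It may fix the operative level and the missing alpha. That limits what can be said about the final analysis, but any level it chooses would still disagree with at least one of these two protocol sections, and Section 14.10 says the analysis follows both documents.

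**Conclusion.** The primary decision rule is wrong as written and must be corrected. The contradiction follows from the printed figures alone and rests on no assumption. Its definite effect is a band of results, 1-sided p from 0.0167 (or 0.0083) to 0.025 on each primary, that can be called met or not met. Its probable effect on sizing is conservative, provided alpha is taken from Section 14.4 as Section 14.2 directs, though the cushion could tip a marginal sample-size estimate over the 300-subject limit.

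The case for correction is the ambiguity of the Phase II rule, not demonstrated loss of error control. Whether the familywise rate is exceeded cannot be settled until the success rule and sidedness are stated.

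**What to change.** State whether the 5% is 1-sided or 2-sided, and whether success means any one primary or all three. Then use one level in Sections 14.2, 14.4 and 14.5, and write the number for alpha in the power formula.
- **(a) Single-endpoint claims.** Use a 98.33% bound (1-sided 5%; F-test alpha 3.33%) or a 99.17% bound (2-sided 5%; F-test alpha 1.67%).
- **(b) All three required.** Declare them co-primary, keep the 1-sided 97.5% interval, delete the 1.67% split, and size at 1-sided 2.5% (F-test alpha 5%).

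Say also whether the 80% power is per endpoint or joint. In Section 14.6, state only whether a secondary group counts solely when fully met; if so, the 97.5% bound can stay.

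**Cost of (a).** The interval half-width grows by 2.128 / 1.960 − 1 = 8.6% or 2.394 / 1.960 − 1 = 22%, and the Phase I gate becomes harder. As an illustration, take 60 completers (120 ratings), an assumed 0.5/0.3/0.2 category split and proportional odds. The Phase I model has no subject term, so its standard error is unpaired: SE(log OR) = √(12 / (120 × (1 − 0.5³ − 0.3³ − 0.2³))) = 0.345. The observed odds ratio needed, exp(ln 0.67 + z × 0.345), rises from 1.32 to 1.40 or 1.53.

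**Cost of (b).** The 12% or 33% cushion is lost. Power returns to 80% per endpoint, and joint power for all three is 51% to 72% at assumed correlations of 0 to 0.9 with equal effects (0.8³ = 0.512 at zero correlation).

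Otherwise the change is wording only.
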